7.2.5.6 Health Economic Outcome Research Assessments

Health-related quality of life (HRQoL) is an important measure of health status or well-being and can be influenced by clinical interventions. It is an important concept used in determining the value of health care services and can serve as a screening tool for identifying physical and psychosocial health concerns from the perspectives of both the child and parent ([Matza et al., 2004](#); [Varni et al., 2005](#)). HRQoL is a multidimensional construct; minimally it includes physical, psychological (including emotional and cognitive), and social health dimensions.

Pediatric Quality of Life Inventory (PedsQL) Infant Scales

In this study, HRQoL will be assessed via the validated Pediatric Quality of Life Inventory (PedsQL) Infant Scales appropriate for the child's age of development ([Varni and Limbers, 2009](#); [Varni et al., 2011](#); [Varni et al., 2001](#)).

The following scales will be used in this study:

- Infant Scale for ages 13-24 months (45 Items)
- Toddler Scale for 2-4 years of age (21 Items)
- Young Child Scale for 5-7 years of age (23 Items)

The PedsQL will be administered to the subject's parent(s) or legally authorized representative(s) and may be conducted via telephone by clinical site staff at the time points specified in the Schedule of Assessments ([Table 1](#)). The scale(s) to be administered at each visit will be specified in the Study Operations Manual.

EQ-5D-5L

The EQ-5D-5L is a standardized measure of health status developed by the EuroQol Group in order to provide a simple, generic measure of health for clinical and economic appraisal ([EuroQol, 1990](#); [Orgeta et al., 2015](#); [Nolan et al., 2016](#)). The EQ-5D-5L provides a simple descriptive profile and a single index value for health status that can be used in the clinical and economic evaluation of healthcare as well as in population health surveys. It consists of a 5-item descriptive system that measures 5 dimensions of the health of the subject's parent(s), including mobility, self-care, usual activities, pain/discomfort, and anxiety/depression. Each dimension is represented by a single item with 5 levels of responses.

The EQ-5D-5L will be administered to the subject's parent(s) or legally authorized representative(s) by site personnel at 24 months CA, 3 years CA, and 4 years CA. Details about the use and administration of the EQ-5D-5L instrument will be provided in the Study Operations Manual.

Health Care Resource Use (HCRU)

To understand the value of the investigational product administered in Study SHP607-202, inpatient and outpatient visits, including visits to specialists, will be recorded at the time points specified in the Schedule of Assessments ([Table 1](#)). Learning support needs and impairment of caregiver productivity will also be assessed.

This assessment may be conducted in person at clinic visits or via telephone by clinical site staff.

Health Utilities Index (HUI)

The Health Utilities Index (HUI) is a family of generic health profiles and preference-based systems used for measuring health status, reporting HRQoL, and producing utility scores.

The HUI2/3 each include a generic comprehensive health status classification system and a generic HRQoL utility scoring system (Horsman et al., 2003). The HUI2/3 will be administered to the subject's parent(s) or legally authorized representative(s) and may be conducted in person at clinic visits or via telephone by clinical site staff at 5 years CA as specified in the Schedule of Assessments (Table 1).

Caregiver Impact Questionnaire (CIQ)

Caregiver burden will be assessed by the CIQ. The CIQ includes 30 items in total and covers the key areas of impact for caregivers, including: 1) impact on relationships, family, social life, and leisure activities; 2) impact on personal time and daily activities; 3) psychological impacts; 4) impact on physical health; and 5) impact on finances and productivity. Data will be collected and summarized descriptively. Results may also contribute to the recommended scoring for studies. The CIQ will be administered to the subject's parent(s) or legally authorized representative(s) and may be conducted via telephone by clinical site staff at the time points specified in the Schedule of Assessments (Table 1).

7.2.5.7 BabyScreen Assessment (Optional)

BabyScreen is an interactive electronic tablet application to evaluate cognitive impairment, used by preterm children at approximately 24 months CA. The tool is engaging, with colorful screens and visual prompts that capture the attention of the child and promote engagement and interaction. Instructions for the site are minimal. The child is encouraged to play with the tablet; no or minimal prompting is needed. This exploratory, optional assessment will be used for validation purposes only, benchmarked against BSID for future use. Participation is limited to selected sites.

7.2.5.8 Spirometry (Optional)

Spirometry will be performed at the 5-year visit. Standard measures will be collected, including forced expiratory volume over 1 second (FEV1) and forced vital capacity (FVC). Participation is optional and has no impact on participating in the main study. Participation is limited to selected sites that have access to personnel with expertise in performing pediatric spirometry.

7.2.6 Cerebral Magnetic Resonance Imaging (Optional)

Participation in the MRI assessment is optional, limited to sites that participated in the MRI assessment in Study SHP607-202, and has no impact on participating in the main study. If consented to, MRI of the brain will be performed.

Volumetric analyses of the cortical gray matter, cortical white matter, corpus callosum, frontal lobes, cerebellum, and total volume will be analyzed for the purposes of this study.

The nature, scope, risks, benefits, and potential sedation associated with the procedure will be explained to the subject and subject's parent(s) or legally authorized representative(s) by the investigator or a designated trained study personnel. Subject's parent(s) or legally authorized representative(s) will be asked to separately opt in or decline participation in this part of the study in the informed consent document.

7.2.7 Safety

7.2.7.1 Medical History

Medical events or conditions should only be captured as medical history if they occur after the end of the subject's participation in the primary Study SHP607-202 and before informed consent in the current Study SHP607-203.

7.2.7.2 Physical Examination

Physical examinations will include a general examination (including assessment of tonsillar hypertrophy) and a neurological examination ([Table 2](#)). Examinations will be performed at the time points specified in the Schedule of Assessments ([Table 1](#)).

Table 2 Assessments for Physical Examinations

General appearance	Cardiovascular
Head and neck	Abdomen
Eyes	Genitourinary
Ears	Skin
Nose	Musculoskeletal
Throat	Neurological
Tonsils	Cerebral palsy (24 months CA only)
Chest and lungs	

7.2.7.3 Blood Pressure, Heart Rate, and Respiratory Rate

Blood pressure, heart rate, and respiratory rate will be measured at the 12-month, 24-month, and 5-year CA visits.

7.2.7.4 Adverse Event Collection

At each study visit, subjects will be questioned in a general way to ascertain if AEs have occurred since the previous visit (eg, "Have you had any health problems since your last visit?"). Please refer to Section [8](#), Adverse and Serious Adverse Events Assessment.

7.2.8 Medication Assessment

All medications received by study subjects will be collected from the time of enrollment through the 5-year CA visit (or upon discontinuation). Any investigational product received by subjects will be recorded separately as part of an assessment of subjects' participation in other clinical studies (Section [7.2.9](#)).

7.2.9 Participation in Other Clinical Studies

Following enrollment, subjects in this study will not be restricted from enrolling in other clinical studies that involve the use of investigational product. The status of a subject's participation in such studies will be recorded (ie, yes/no). If a subject is enrolled in such a study, additional parameters will be recorded, including the masking status of the study, the identity of the investigational product or treatment being evaluated in the study, and the subject's treatment assignment in the study (if possible).

7.2.10 Appropriateness of Measurements

Overall, the primary and secondary efficacy and safety measures being employed in this study are considered appropriate for the follow-up of preterm infants. The validated tools being used to assess neurodevelopment, physical development, and health economic research outcomes in this pediatric population are widely used and recognized.

In some cases, tools were designed specifically for use in this study, namely, the pulmonary morbidity questionnaire. In this case, the assessment is based on published research in a similar pediatric population ([Pryhuber et al., 2015](#)).

8. ADVERSE AND SERIOUS ADVERSE EVENTS ASSESSMENT

8.1 Definition of Adverse Events, Period of Observation, Recording of Adverse Events

According to the International Conference on Harmonization (ICH), an AE is "any untoward medical occurrence in a patient or clinical investigation subject administered a pharmaceutical product and which does not necessarily have a causal relationship with treatment. An AE can therefore be any unfavorable and unintended sign (including an abnormal laboratory finding), symptom, or disease temporally associated with the use of a medicinal (investigational) product, whether or not related to the medicinal (investigational) product" (ICH Guidance E6 [R2] 2016).

In this long-term outcome study in follow-up to Study SHP607-202, no investigational product is being administered; it is therefore a non-interventional study. However, it seeks information on whether prior administration of IMP in Study SHP607-202 impacts long-term outcomes.

For the purposes of this study only the following AEs will be collected:

- Specified targeted medical events (Section 8.1.4)
- AEs related to investigational product
- AEs leading to withdrawal from the study
- Serious AEs that occur during the study period or were previously present and worsen during the study period.

All AEs described above are collected from the time the informed consent is signed until the defined follow-up period stated in Section 3.2. Where possible, a diagnosis rather than a list of symptoms should be recorded. If a diagnosis has not been made, then each symptom should be listed individually. All AEs described above should be captured on the appropriate AE pages in the CRF and in source documents.

All AEs must be followed to closure (the subject's health has returned to his/her baseline status or all variables have returned to normal), regardless of whether the subject is still participating in the study. Closure indicates that an outcome is reached, stabilization achieved (the investigator does not expect any further improvement or worsening of the event), or the event is otherwise explained. When appropriate, medical tests and examinations are performed so that resolution of event(s) can be documented.

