Study SHP607-202 is a Phase 2b, multicenter, randomized, open-label, controlled, 3-arm study that is being initiated to evaluate the clinical efficacy and safety of SHP607 in preventing chronic lung disease through 12 months CA compared to standard neonatal care in extremely premature infants. Approximately 477 subjects with GA of 23 weeks +0 days to 27 weeks +6 days will be randomized in a 1:1:1 ratio to receive either SHP607 at 250 µg/kg/24 hours, SHP607 at 400 µg/kg/24 hours, or standard neonatal care alone. Subjects randomly assigned to treatment will receive continuous IV infusion of study drug commencing within 24 hours of birth, once all baseline assessments have been completed. The infusion of study drug will continue to PMA 29 weeks +6 days. The primary objective of the study is to assess the effect of SHP607 on reducing the burden of CLD, as indicated by a reduction in time to final weaning off respiratory technology support (RTS) through 12 months CA, as compared to a standard neonatal care group.

Study SHP607-202 will evaluate the clinical efficacy and safety of SHP607 in preventing chronic lung disease through 12 months CA compared to standard neonatal care in extremely premature infants. Although treatment with SHP607 in Study SHP607-202 represents a short-term exposure (<2 months for each subject), SHP607 may have long-lasting effects on respiratory outcomes as well as other potential outcomes related to complications of prematurity such as neurodevelopment, vision, and growth impairments. In addition, it is critical to understand any long-term safety effects from short-term exposure to SHP607. The purpose of Study SHP607-203 is to evaluate the long-term safety and efficacy outcomes in subjects who received short-term treatment with SHP607 in Study SHP607-202.

The assessment tools used in this study will be different from those used in Study SHP607-202, given the changes in physical and cognitive development that will occur in the subjects as they age during their participation in this study.

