7. STUDY PROCEDURES

7.1 Study Schedule

See [Table 1](#) for study procedures. The timing of all study visits is based on subjects' CA.

Although Study SHP607-202 is open-label, measures will be instituted in Study SHP607-203 to blind selected site personnel who are involved in efficacy assessments in order to minimize bias in study outcomes. Site personnel who administer the following study assessments will be blinded to the treatment status of each subject: BSID, KSPD, WPPSI, GMFM-88, spirometry, and MRI. Families will be instructed not to discuss treatment assignment with the assessors. The assessors will not be part of the study team or participate in study team meetings. The Sponsor will work with each site to clarify the process for blinding and each site will document the manner in which blinding will be maintained at the site.

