8.1.2 Relationship Categorization

A physician/investigator must make the assessment of relationship to prior investigational product for each AE. The investigator should decide whether, in his or her medical judgment, there is a reasonable possibility that the event may have been caused by the investigational product. If there is no valid reason for suggesting a relationship, then the AE should be classified as “not related”. Otherwise, if there is any valid reason, even if undetermined or untested, for suspecting a possible cause-and-effect relationship between the investigational product and the occurrence of the AE, then the AE should be considered “related”. The causality assessment must be documented in the source.

The following additional guidance may be helpful:

Related	The temporal relationship between the event and the administration of the investigational product is compelling enough and/or follows a known or suspected response pattern to that product, and the event cannot be explained by the subject’s medical condition, other therapies, or accident.
Not related	The event can be readily explained by other factors such as the subject’s underlying medical condition, concomitant therapy, or accident and no plausible temporal or biologic relationship exists between the investigational product and the event.

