8.1.4 Targeted Medical Events

If it is determined that any of the following targeted medical events have been experienced by a subject, they will be recorded as AEs or SAEs (refer to Section 8.2.3), as appropriate, regardless of relationship to prior investigational product (SHP607 as administered in Study SHP607-202):

- Intracranial hypertension
- Any abnormality of glucose metabolism (eg, hypoglycemia, hyperglycemia, and diabetes)
- Tonsillar hypertrophy (based on tonsil examination [part of the physical examination])
- Increased cardiac size

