8.2.5 Serious Adverse Event Onset and Resolution Dates

The onset date of the SAE is defined as the date the event meets serious criteria. The resolution date is the date the event no longer meets serious criteria, the date the symptoms resolve, or the date the event is considered chronic. In the case of hospitalizations, the hospital admission and discharge dates are considered the onset and resolution dates, respectively.

In addition, any signs or symptoms experienced by the subject after signing the informed consent form, or leading up to the onset date of the SAE, or following the resolution date of the SAE, must be recorded as an AE, if appropriate.

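### SAP 7.1 pools non-serious AEs that could be collected only if judged related to SHP607 into by-group tables, although standard-care children could not enter by that route (minor)

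*Protocol*

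**What the plan says.** Protocol 8.1 limits collection: "For the purposes of this study only the following AEs will be collected". The four routes are specified targeted medical events, "AEs related to investigational product", events leading to withdrawal, and serious events.

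The product meant is the one given earlier. Protocol 8.1.4 requires targeted events to be recorded "regardless of relationship to prior investigational product (SHP607 as administered in Study SHP607-202"), and SAP 7.1 ties the related category to the antecedent study. SAP 7 analyses safety by the treatment actually received there, so the standard-care column holds children who had no SHP607.

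Protocol 8.1.2 asks the investigator to call an event related "if there is any valid reason, even if undetermined or untested, for suspecting a possible cause-and-effect relationship" between product and event. Its additional guidance is stricter. It looks for compelling timing and/or a known or suspected response pattern, and for the absence of another explanation such as the child's condition or other treatment. Protocol 7.1 blinds only named assessors: staff giving the listed tests "will be blinded to the treatment status of each subject: BSID, KSPD, WPPSI, GMFM-88, spirometry, and MRI". The relatedness judgement is not on that list.

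SAP 7.1 presents all collected AEs by treatment group: an overall summary (including Any AE and Any severe AE), SOC/PT, maximum severity, and preferred terms reaching 5% in any arm. There are separate tables for related AEs, SAEs, AEs leading to death, AEs leading to discontinuation, and AEs of important potential risks.

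**The concern.** Comparing long-term safety with standard neonatal care is a primary objective (Protocol 2.1.1), and Protocol 9.8 bases the primary safety analysis on AEs reported in the study. SAP 6 drops all efficacy analysis, so safety is the only comparison left.

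A comparison of AE rates between arms assumes that the same event would be recorded in either arm. Here one of the four routes depends on having received SHP607. A non-serious, non-targeted event that does not lead to withdrawal can be recorded in an SHP607 child, if the investigator suspects the drug, but not in a standard-care child. Someone who knows the treatment decides this, and the resulting events are counted in the same rows as events collected equally in all arms. Neither document tells the reader that these events could not be collected under standard care.

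**Working it through.** The plan gives no figure on this point to reproduce. The check traces the collection rule into the tables and then sizes the effect.

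**1. Is the route closed to standard care?** By inference, yes; no sentence says so. SAP 9.2.3 imputes a missing relationship as related in any arm, but this only relabels an event already collected. Protocol 8.2.5 can add non-serious events, namely "any signs or symptoms experienced by the subject after signing the informed consent form, or leading up to the onset date of the SAE", but it does so in every arm.

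**2. Which tables carry these events?**
- Affected: Any AE, Any severe AE, SOC/PT, maximum severity, most frequent.
- Possibly affected: important potential risks. The SAP's preferred-term list includes snoring, hypoacusis, ear tube insertion and thymus enlargement, none of them named in Protocol 8.1.4. A non-serious event with such a term could be on file only because it was judged related. It would sit in that table's non-serious, related cells.
- Unaffected: SAEs, deaths, discontinuations.

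**3. Direction of each kind of error.**
- Unrelated event judged related, collected only by this route: moves the pooled tables against SHP607.
- Related event judged related: a drug effect, not bias.
- Related non-serious event judged unrelated: not collected, so it favours SHP607. Illustration (assumed rates): with 40% having an AE by the shared routes and 10% a truly related one, the true excess is (1 − 0.40) × 0.10 = 6.0 points. If half are missed, it is (1 − 0.40) × 0.05 = 3.0 points.
- SAE, targeted event or withdrawal event wrongly called related: collected anyway, so no all-AE count changes.

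**4. Expected size with no drug effect.** Let p be the share of each group with an AE from a shared route, and q the share of SHP607 children with a wrongly attributed related-only AE. The documents give neither. Assuming independence, the excess is 1 − (1 − p)(1 − q) − p = (1 − p)q.

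| q (assumed) | p = 20% | p = 60% |
|---|---|---|
| 0.5% | 0.4 points | 0.2 points |
| 1% | 0.8 points | 0.4 points |
| 2% | 1.6 points | 0.8 points |

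Larger values need heavy over-attribution. If 90% of children have some other non-serious AE and a share f of those children have one wrongly judged related, then q = 0.9f. At p = 40% the excess is 0.6 × 0.9 × 0.05 = 2.7 points at f = 5%, and 5.4 points at f = 10%.

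**5. Why q is probably low.** Protocol 1.3 states "The infusion of study drug will continue to PMA 29 weeks +6 days". Taking term as 40 weeks (assumed), that leaves 40 weeks − 29 weeks 6 days = 10.1 weeks, about 2.3 months, before term. Collection starts at about 12 months CA, so the gap is about 14.3 months.

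**6. Size in the study as terminated.** SAP 3.1 puts enrolment below 10% of the plan: 0.10 × 477 = 47.7, so at most 47 children. With a 1:1:1 split (assumed), that is 47/3 ≈ 16 per arm and 47 × 2/3 ≈ 31 on SHP607. The chance that none of the 31 is affected is (1 − q)^31: 85.6% at q = 0.5%, 73.2% at 1%, 53.5% at 2%. If one child is affected and has no other collected AE, that arm's Any AE rate rises by 1/16 = 6.25 points. One child also puts a preferred term in the 5% table in any arm of 20 or fewer (1/20 = 5.0%; 1/21 = 4.8%).

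**7. After the fix.** If the comparison is limited to routes open to every arm, the expected difference with no drug effect is 0 for every p and q.

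**The case against.** The case for leaving the plan alone is substantial, and most of it stands.

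- A reader might infer that every wrong attribution counts against SHP607. The documents do not support that. As step 3 shows, missed related events favour SHP607, and mislabelled serious or targeted events change no all-AE count.
- The low threshold in Protocol 8.1.2 is only part of that section. The guidance beside it points towards not related in an extremely preterm child more than a year after infusion. This lowers the likely rate, but it does not close the route, because a suspected response pattern can stand in for timing.
- The related-AE table and listing, and the relationship split in the important-risk table, let a reader find such events among at most 47 children. The Any AE row is also labelled as restricted to the Protocol 8.1 list. This is only partial exposure: the related-AE table also holds related serious and targeted events, no all-AE table is shown without this route, and nothing says that standard care could not contribute.
- The 6-point jump and the crossing of 5% are not peculiar to this route. Any single event in any arm of about 16 does the same.
- The tables are descriptive, with no tests, so there is no error rate to inflate.

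These points reduce the severity. They do not remove the asymmetry in what is counted.

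**Conclusion.** The asymmetry is real and follows from Protocol 8.1 read with SAP 7.1. Unrelated events wrongly judged related and collected only by that route push the pooled by-group AE tables against SHP607.

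A reader might go further and conclude that the AE tables as a whole are biased against SHP607, or that a spurious excess should be expected. The documents do not support either. The SAE, death and discontinuation tables do not depend on this route, correct attributions are drug effects, the opposite error favours SHP607, and there may be no such event at all.

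On the assumed q of 0.5% to 2% and p of 20% to 60%, the expected excess in Any AE is 0.2 to 1.6 points. This rests on independence of the routes, an even split of at most 47 children, and rates that the documents do not give. Severity: minor.

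**What to change.** In SAP 7.1:

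1. Keep all planned tables and listings.
2. Add by-group Any AE, Any severe AE and SOC/PT summaries restricted, in every arm and regardless of relatedness, to events that are serious, led to withdrawal, or fall in a Protocol 8.1.4 category. That section covers "Any abnormality of glucose metabolism (eg, hypoglycemia, hyperglycemia, and diabetes"), so hyperglycemia and diabetes must be counted even though the SAP's preferred-term list omits them. Use these summaries for the comparison with standard care.
3. Show related events outside these three routes separately for the SHP607 groups.
4. Footnote the all-AE and important-potential-risk tables to say that such events could not be collected under standard care, or that none occurred. If none occurred, the footnote alone is enough.

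Non-serious signs or symptoms of an SAE recorded under Protocol 8.2.5 drop out of the restricted summaries equally in all arms. Neither document shows a field linking them to the SAE, so the rule does not try to identify them. A related one would appear under item 3, and the footnote should allow for that exception.

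Cost: SAP text, a mapping of preferred terms to the Protocol 8.1.4 categories, and a few more descriptive tables in an abbreviated report. No new data or protocol amendment is needed. The restricted summaries leave out correctly attributed non-serious drug effects, so they must be read alongside the all-AE and related-AE tables.
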